Competency-Based Medical Education (CBME), focused on core competencies, is the current trend in medical education. Entrustable Professional Activities (EPAs) describe clinical tasks that interns are deemed competent to perform independently by the end of each training stage (Fu et al., 2023). EPAs, developed by Dutch medical education scholar Olle ten Cate from 2005 onwards, provide a curricular and assessment framework where supervision levels reflect intern competence and trustworthiness in clinical performance (ten Cate et al., 2015). Different medical professions in Taiwan have begun developing their own EPAs. For occupational therapy, under the facilitation of the Taiwanese Occupational Therapy Association, hospitals have started pilot EPA-based clinical assessments and research dissemination (Fu et al., 2023). In the field of physiological occupational therapy, three EPAs exist for hospital use: performing occupational therapy assessment, performing occupational therapy interventions, and providing health education and counseling.

Therefore, the ultimate goal during clinical internships is for students to acquire core competencies and translate them into workplace competencies. To determine if occupational therapy interns meet these goals, we need to use both Mini-CEX and EPAs. This study aims to examine the impact of using these two tools clinically to assess interns' ability to practice independently and whether correlations exist between subscale scores.

5、 Objectives: This study aims to investigate the effects of combining Mini-CEX and EPAs on evaluating interns' independent practice capability and the correlations between scale sub-items. It is expected that students performing well on EPAs and Mini-CEX will demonstrate better clinical performance and operational skills during internships. We hope EPAs will provide stronger evidence of interns' readiness to independently perform medical tasks.

6、 Methods:

(1) Selection criteria and sample size:

(a) Sample size: 50 subjects at Far Eastern Memorial Hospital; 0 at other centers

(b) Inclusion criteria:

(i) Occupational therapy interns in the physical domain at Far Eastern Memorial Hospital

(ii) Provide informed consent to participate

(c) Exclusion criteria: None

(d) Recruitment: Interns in the physiological domain will be recruited during the 6th week of their internship; assessment will be conducted in the 8th week.

(e) Study design:

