This is a cross-sectional study involving physiotherapy interns receiving clinical training.

After obtaining consent at week 6, assessments using EPAs and Mini-CEX will be conducted

during the 8th week in the ward. Each assessment takes about 20 minutes. Results will be analyzed two weeks after submission of instructors' internship grades. Since the occupational therapy department covers physiological and pediatric domains with different clinical instructors, pediatric instructors provide consent forms and explain the study to physiological interns. Participation is voluntary and will not affect internship coursework or rights.

(f) Follow-up or rehabilitation plan:

Subjects will follow routine clinical training; EPA and Mini-CEX are routine tests at week 8.

No additional follow-up or rehabilitation needed.

(g) Outcome measures and statistical analysis:

(i) Clinical performance evaluated by Mini-CEX and EPAs

(ii) Statistic analysis:

Descriptive statistics for demographics; Pearson's correlation to explore relationships between variables; multiple linear regression analyses for predictors of clinical performance including age, gender, average self-study time, prior university experience, parents' occupations, and residence. Significance set at $p < 0.05$.

(h) Questionnaires and data collection:

(i) Demographics collected by semi-structured questionnaire covering age, gender, average self-study time, prior university experience, parents' occupation, and residence.

(ii) Mini-Clinical Evaluation Exercise (Mini-CEX):

Developed by Norcini et al. (1995) and officially translated and authorized for use in Taiwan since 2004 (Chen, 2007), the Mini-CEX assesses clinical diagnostic skills of medical interns using structured forms and immediate feedback. The assessment covers seven core competencies and is scored on a scale from 1 to 9 for each item, where higher scores indicate better clinical performance. This tool has demonstrated good reliability and validity (Holmboe et al., 2003).

(iii) Entrustable Professional Activities (EPAs):

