Developed by Olle ten Cate starting in 2005 (ten Cate et al., 2015), EPAs evaluate intern competence according to supervision levels required to perform professional tasks safely. Scores typically range from 1 to 5, with higher values indicating greater independence and readiness to carry out clinical activities autonomously. In Taiwan, EPAs have been progressively developed for various medical specialties, including occupational therapy. Promoted by the Taiwanese Occupational Therapy Association, initial pilot studies have been reported (Fu et al., 2023). This study specifically utilizes EPAs related to occupational therapy assessment tasks in the physiological domain.

(2) Duration and schedule:

Five physiological interns per rotation, three rotations per year (approx. 15 participants/year), with enrollment and data collection planned over four years.

(3) Research personnel, roles, and equipment:

No.	Name	Role	Responsibilities
1	[name]	Principal Investigator	Proposal submission, IRB application, progress monitoring
2	[name]	Co-Investigator	Joint planning, writing, materials preparation, data collection and analysis
3	[name]	Co-Investigator	Joint planning, writing, materials preparation, data collection and analysis
4	[name]	Co-Investigator	Joint planning, writing, materials preparation, data collection and analysis
5	[name]	Co-Investigator	Joint planning, writing, materials preparation, data collection and

			analysis
6	[name]	Co-Investigator	Joint planning, writing, materials preparation, data collection and analysis
7	[name]	Co-Investigator	Joint planning, writing, materials preparation, data collection and analysis

7、 Handling of research materials:

(1) Collection and management during study:

- (a) Paper records will be archived in locked cabinets accessible only to the principal investigator.
- (b) Electronic data will be encrypted and stored on Google Drive, password known only by the principal investigator.

(2) Post-study handling and storage duration:

- (a) Paper records archived securely in locked cabinets for 7 years, access restricted to principal investigator only.
- (b) Electronic data stored encrypted on designated computers, de-identified by replacing names with study codes. Password access limited to the principal investigator; others require PI's permission. Data will be securely destroyed by the principal investigator after 7 years.

8、 Protection of participant rights:

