(1) Potential physical, psychological, or social harm and remedies:

- No risks expected as participants only need to complete questionnaires.

(2) Conditions and mechanisms for suspension/termination or withdrawal:

- Participants may withdraw at any time if concerns arise, with assurance that withdrawal will not affect internship rights or coursework.

(3) Participant compensation: None.

9、 Expected outcomes:

(1) This study aims to explore the combined use of Mini-CEX and EPAs for assessing interns' independent functioning and correlations between subscale scores, expecting positive correlation between EPA/Mini-CEX performance and clinical skills. This may confirm intern competency for independent practice.

(2) Research ownership and utilization:

- Results belong to the Rehabilitation Department of Far Eastern Memorial Hospital. Findings may be used by occupational therapy clinical instructors to improve teaching effectiveness.

10、 Funding and budget:

- Internal research grant (Project No.: FEMH-2025-C-091)

Item	Description	Amount (NTD)
Operational expenses	Consumables, supplies, books, and miscellaneous (including study personnel costs, wages, labor insurances, health insurances, and labor pension contributions)	135,000
Management fee	10% of operational expenses	13,500
Total		148,500

11、 Conflict of interest:

- This study is solely an internal initiative for new domain research within the unit, with no external collaborations, commercial involvement, or patent issues.

12、 References:

Fu, C. P., Chiang, F. M., Lee, C. Y., Chi, H. Y., Wu, J. L., Lin, Y. J., Li, M. W., Chen, Y. J., Chang, W. Y., Chang, W. D., Huang, S. M., Liao, W. S., Yang, Y. C., Huang, C. K., Kuo, N. J., Liu, T. H., & Chen, Y. L. (2023). Developing the topics of entrustable professional activities in pediatric

occupational therapy in Taiwan: A pilot study. *Taiwan Journal of Occupational Therapy*, 41(2), 91–110. [https://doi.org/10.6594/tjot.202308_41\(2\).0001](https://doi.org/10.6594/tjot.202308_41(2).0001)

Norcini, J. J., Blank, L. L., Duffy, F. D., & Fortna, G. S. (2003). The mini-CEX: a method for assessing clinical skills. *Ann Intern Med*, 138(6), 476-481. <https://doi.org/10.7326/0003-4819-138-6-200303180-00012>

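### Section 9(1) reads competency for independent practice from a correlation, which carries no information on the EPA level that interns reach

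*Protocol*

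**What the plan says.** Section 5 of the Protocol (Objectives) has two strands: how combining Mini-CEX and EPAs serves to evaluate whether interns can practise independently, and how the sub-items of the two scales correlate. It also hopes that EPAs will give stronger evidence of readiness.

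Section 9(1) repeats both strands, "expecting positive correlation between EPA/Mini-CEX performance and clinical skills", and its next sentence is "This may confirm intern competency for independent practice".

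The analyses named in 6(1)(g)(ii) are:

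- "Descriptive statistics for demographics";
- "Pearson's correlation to explore relationships between variables";
- "multiple linear regression analyses for predictors of clinical performance", where the predictors are background variables such as age, gender and self-study time.

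Section 6(1)(g)(i) names Mini-CEX and EPAs as the measures of clinical performance. No separate measure of clinical skills is named. On the EPA scale, 6(1)(h)(iii) says: "Scores typically range from 1 to 5, with higher values indicating greater independence". No level is identified as independent practice. On timing, 6(1)(d) says that "assessment will be conducted in the 8th week", and 6(1)(f) plans no further follow-up.

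**The concern.** Section 9(1) moves from an association to a statement about attainment. On the protocol's own description of the EPA scale, readiness is how high an intern stands. A correlation describes whether interns who stand higher on one score also stand higher on another. It does not say where the group stands.

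Two features make this more than loose phrasing. First, the clinical performance that the tools are meant to relate to is itself scored by those tools, so a positive correlation mainly shows agreement between two ratings made in the same week. Second, none of the analyses named in 6(1)(g) summarises the EPA level reached, so nothing there would correct the inference.

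The independent-practice strand of the objectives is at stake. A reader of the results, including the clinical instructors whom 9(2) names as possible users, could take a strong correlation as evidence of readiness when few or no interns had been rated at a high level.

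**Working it through.** The protocol gives no figure to reproduce here. The check is whether r can carry information on level, and what a summary of level would look like at the planned size.

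**Inputs from the Protocol.** n = 50 (6(1)(a)); EPA scores typically 1 to 5 (6(1)(h)(iii)); Mini-CEX items 1 to 9 (6(1)(h)(ii)); Pearson correlation (6(1)(g)(ii)).

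**Inputs assumed.** The illustrative scores, level 4 as a marker of high entrustment, and the counts reaching a level are chosen only to show the arithmetic. The protocol gives none of them.

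**Step 1: r does not depend on level.** For EPA scores x and Mini-CEX scores y,

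r = Σ(x − x̄)(y − ȳ) / √[Σ(x − x̄)² · Σ(y − ȳ)²].

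Replace each x by x + c. The mean becomes x̄ + c, so each deviation is (x + c) − (x̄ + c) = x − x̄. Every term is unchanged, and so is r. The same holds for a constant added to y.

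**Step 2: illustration with 50 interns.** Take 19 interns at EPA level 1, 14 at level 2 and 17 at level 3. The mean is (19×1 + 14×2 + 17×3)/50 = 98/50 = 1.96. Mini-CEX scores were simulated to rise with EPA level, with random scatter, and both scores were then moved up by 0, 1 or 2 points.

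| Points added | EPA range | Mean EPA | At level 4 or above | r |
|---|---|---|---|---|
| 0 | 1–3 | 1.96 | 0/50 = 0% | 0.705 |
| 1 | 2–4 | 2.96 | 17/50 = 34% | 0.705 |
| 2 | 3–5 | 3.96 | (14+17)/50 = 62% | 0.705 |

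One value of r fits a group in which nobody has reached level 4 and a group in which most have.

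**Step 3: the regression does not fill the gap.** Adding a constant to the outcome moves only the intercept. The slopes for the background predictors and their p-values stay the same, so these results do not tell the reader how many interns reached a given level.

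**Step 4: what a level summary would give.** If x of 50 interns are at or above a chosen level, the exact (Clopper-Pearson) 95% limits are

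lower = Beta quantile 0.025 with parameters (x, 50 − x + 1); upper = Beta quantile 0.975 with parameters (x + 1, 50 − x).

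| x | Proportion | Exact 95% CI |
|---|---|---|
| 10 | 20% | 10.0% to 33.7% |
| 25 | 50% | 35.5% to 64.5% |
| 40 | 80% | 66.3% to 90.0% |
| 45 | 90% | 78.2% to 96.7% |

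These intervals show the precision available for the readiness question from scores already collected. They do not measure the size of an error in the plan.

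**The case against.** The best defence is that 9(1) is hedged and sits under expected outcomes. It is not a hypothesis or a decision rule, and no section makes competency depend on a significant r. A reader might infer that the study will declare competency confirmed. The text does not go that far. The hedge does not rescue the logic, however, because a correlation of any size is silent on level.

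It can also be said that the sentence refers back to the whole combined assessment and not only to the correlation, and that section 5 ties readiness evidence to the EPAs themselves. That reading is possible. But the correlation is what immediately precedes the sentence, and it is the only result 9(1) anticipates.

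Third, the demographics phrase in 6(1)(g)(ii) is not written as exclusive, EPA scores are a named outcome, and score summaries and cut-offs are often left to an SAP, which is not at hand. A reader might infer that no level summary will ever be produced. The document does not establish that. The point therefore rests on the inference written in 9(1), which an SAP table would not remove.

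Fourth, a reader might infer that the week-8 assessment conflicts with the background definition of EPAs as "clinical tasks that interns are deemed competent to perform independently by the end of each training stage". The documents do not support this. Neither the rotation length nor the training-stage length is given, the two are not equated, and week 8 may be the end of the stage.

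Finally, nothing shows that the department already has a level that it treats as independent, so the fix cannot presume one.

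**Conclusion.** The point holds for the stated inference. A positive correlation between EPA and Mini-CEX scores can show that the tools agree. It cannot confirm, or make more likely, that interns are competent to practise independently. The size is best seen in the illustration: the same r of 0.705 is compatible with 0%, 34% or 62% of interns at level 4 or above. The algebra in step 1 needs no assumption. The percentages depend on invented scores and on level 4 as an arbitrary marker.

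The fault lies in the conclusion and the named analyses, not in the instrument: EPA scores express a level and could answer the question if reported as such. The correlation stays valid for the association aim. The change should be made, but it does not threaten the study's conduct or its data. No claim is made that the week-8 timing is wrong.

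**What to change.** **Section 9(1).** Limit the conclusion from the correlation to association. For example: *a positive correlation would indicate that EPA and Mini-CEX ratings agree; it would not by itself show that interns are competent to practise independently.*

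**Section 6(1)(g).** For the readiness aim, add the distribution of EPA levels and the proportion of interns at or above a stated level, with an exact 95% confidence interval. The department should choose that level and write it down before data are examined. If an intern receives more than one EPA rating, the rule for combining them should be fixed at the same time. Describe the result as status at week 8, on the assessment-task EPAs that 6(1)(h)(iii) says are used.

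**Cost.** No new data are needed, because 6(1)(f) says both tools are already routine at week 8. The change is one descriptive result and a few lines of text. The small downside is that a level must be fixed in advance and the claim becomes narrower.
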